#### 4.8.6. Multiplicity Adjustments

All statistical inference will be 2 sided at a 0.1 level of significance. To control the overall Type I error rate, a hierarchical testing approach as illustrated in Figure 2 will be applied to the statistical testing of

Morphic Therapeutic, Inc.  
Study Number: MORF-057-202

[figure not shown]
Statistical Analysis Plan  
Version 1.0, 16SEP2024

the primary and secondary endpoints for comparisons of each MORF 057 dose group with the placebo group.

First, for the primary efficacy endpoint of clinical remission at Week 12, the Hochberg method will be applied to the comparisons of 200 mg B.I.D. with placebo and 100 mg B.I.D. with placebo. If both p values are  $<0.1$ , both doses will be declared significant. If one of the p values is  $\geq 0.1$ , the other p value will be tested at a 0.05 significance level and the corresponding dose will be declared significant only if the p value is  $<0.05$ . If both p values are  $\geq 0.1$ , no dose will be declared significant, and no further formal testing will be performed.

If both 200 mg B.I.D. and 100 mg B.I.D. achieved the statistical significance for the primary efficacy endpoint, the fixed sequence method will be used to test the comparison of 100 mg Q.D. with placebo for the primary efficacy endpoint and the comparison of each dose with placebo for the secondary efficacy endpoint of clinical response at Week 12 in a predefined order as specified in [Figure 2](#) below. All tests will be performed at the same significance level alpha=0.1, with the moving to a second test only after a success, i.e., p value  $<0.1$ , on the previous test. Further testing stops as soon as one test in the sequence fails to meet significance, i.e., p value  $\geq 0.1$ .

The testing of the exploratory efficacy endpoints not included in the hierarchical procedure will be used for exploratory purposes only.

**Figure 2: Hierarchical Testing Procedure**

## 4.9. Safety Analysis

All safety analyses will be performed based on the safety data collected during the on-treatment period, which is defined as the period from the administration of the first dose of study drug up to 7 days after the last dose of study drug, unless specified otherwise. The safety data will be summarized by treatment groups and the pooled MORF-057 groups based on the Safety Population defined in Section 3.3.

The safety analysis for the Induction Period will include the safety data collected during the 12-week Induction Period (see Section 1.5.1). If participants start their maintenance treatment before completing all safety assessments at Visit 5 (Week 12) due to a protocol deviation, clinical laboratory tests, vital signs and ECG at Week 12 visit will still be included in the 12-week Induction Period Analysis, even if they are measured after the participants start their maintenance dose.

The safety analysis for the 52-week Treatment Period will include cumulative safety data collected during the entire 52-week Treatment Period for the treatment groups randomized to an active MORF-057 dose. For the treatment group initially randomized to placebo and subsequently switched to an

Morphic Therapeutic, Inc.  
Study Number: MORF-057-202

Statistical Analysis Plan  
Version 1.0, 16SEP2024

active MORF-057 dose for maintenance treatment, only safety data collected during the 40-week Maintenance Period will be included for the participants in this group who have continued to the Maintenance Period and received MORF-057, as described in Section 1.5.2.

The safety analysis for the 104-week Total Treatment Period will include cumulative safety data collected during the entire 104-week Total Treatment Period for the treatment groups initially randomized to an active MORF-057 dose. For the treatment group initially randomized to placebo and subsequently switched to an active MORF-057 dose for maintenance treatment, only safety data collected during the 40-week Maintenance and 52-week Extension Periods will be included for the participants in this group who have continued to the Maintenance Period and received MORF-057, as described in Section 1.5.3.

In all safety summaries by treatment groups for the 52-week Treatment Period Analysis and the 104-week Total Treatment Period Analysis, participants initially randomized to an active MORF-057 treatment group will be categorized in the treatment group based on their actual MORF-057 dose received during the Induction Period, regardless of the actual maintenance MORF-057 dose. If any participants have their actual MORF-057 dose during the Maintenance/Extension Period different from the maintenance dose planned for the treatment group in which they are included in the analysis, additional summaries or listings may be provided for them as appropriate.

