## 1.2. Study Design

This study is a randomized, double-blind, placebo controlled, multicenter, Phase 2b study to evaluate the efficacy and safety of 3 active dose regimens of MORF-057 (as capsule, P.O.) versus matching placebo in study participants with moderately to severely active UC.

Approximately 280 participants will be randomized into the treatment groups in a 1:1:1:1 ratio (i.e., 70 participants per group). The study will enroll participants who are advanced therapy naïve (i.e., have no previous exposure to an advanced therapy treatment for UC) and advanced therapy experienced (excluding vedolizumab), with at least 30% but no more than 40% of advanced therapy experienced participants. Randomization stratification factors will include baseline MES (<3 vs 3) and previous use of advanced therapy treatment (advanced therapy naïve vs advanced therapy experienced). All participants will be enrolled from approximately 150 centers worldwide. For this study, moderately to severely active UC will be defined as having an mMCS of 5 to 9 (inclusive), with an MES  $\geq 2$  (confirmed by central reader).

The main part of this Phase 2b study will consist of a Screening Period (up to 6 weeks, consisting of Stage 1 and Stage 2 testing), a Treatment Period (52 weeks, including a 12-week Induction Period and a 40-week Maintenance Period), and a Safety Follow up (SFU) Period (4 weeks).

During the main part of this study, there will be approximately 11 scheduled study visits: Screening Visit(s) (Visit 1 at Weeks 6 to 1), multiple Treatment Visits (Visits 2-10 at Weeks 0, 2, 6, 12, 18, 24, 32, 42, and 52 [End of Treatment (EOT)]), and an SFU Visit (visit to occur 4 weeks after the last dose of study drug is received, which will be at Week 56 if the full Treatment Period is completed or earlier if treatment is discontinued early). Study Day 1 represents the first day of the Treatment Period (i.e., when the participant will receive the first dose of study drug).

All participants who complete the 52-week Treatment Period will have the opportunity to continue their treatment in a 52-week Maintenance Extension Period.

During the optional Maintenance Extension, there will be 5 scheduled visits: 4 Treatment Visits (Visits 11-14 at Weeks 65, 78, 91, and 104 [EOT]) and an SFU Visit (visit to occur 4 weeks after the last dose of study drug is received, which will be at Week 108 if the full Maintenance Extension is completed or earlier if treatment is discontinued early).

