### 1.3. Sample Size and Power

The sample size was determined based on the primary endpoint of clinical remission at Week 12 by using the Chi-Squared Test to compare two proportions. A sample size of 70 participants per group (giving a total of 280) will provide 80% power to detect a difference of 15% in the clinical remission rate between MORF-057 and placebo, based on the use of a two-sided test at the alpha=0.10 level of significance. The calculation is based upon an assumed placebo remission rate of 7%.

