#### 4.6.1.2. Treatment Exposure for the 52-week Treatment Period

For participants who are randomized to an active MORF-057 treatment group (Group 1, Group 2 and Group 3 in [Table 3](#)) and have received at least one dose of MORF-057, the cumulative treatment exposure to MORF 057 during the 52-week Treatment Period, including the exposure during the Induction Period, will be summarized by treatment groups based on the actual MORF-057 dose received during the induction period. The duration of treatment exposure for 52-week Treatment Period will be calculated as:

- Days = last dose date on 52-week Treatment – first dose date of induction treatment + 1

Morphic Therapeutic, Inc.  
Study Number: MORF-057-202

Statistical Analysis Plan  
Version 1.0, 16SEP2024

The last dose date on 52-week Treatment will be the date of last treatment recorded on the EOT eCRF page for the main part of the study (i.e., 52-week Treatment Period).

For participants who are initially randomized into the placebo group and subsequently switched to MORF-057 200 mg Q.D. -E for maintenance treatment, the summary of treatment exposure for the 52-week Treatment Period will include only the exposure to MORF-057 during the Maintenance Period. The duration of exposure will be based on the number of days they received MORF-057 during the Maintenance Period, which will be calculated as:

- Days = last dose date on 52-week Treatment – first dose date of maintenance treatment + 1

The last dose date on 52-week Treatment will be the date of last treatment recorded on the EOT eCRF page for the main part of the study. The first dose date of maintenance treatment will be the Maintenance Period First Dose date recorded on the Study Period Transition eCRF page.

Duration of treatment exposure (days) will be summarized using continuous descriptive statistics, and also summarized categorically by counts and percentage for each of the following categories and cumulatively according to these categories:

- 1 to 42 days
- 43 to 84 days
- 85 to 182 days
- 183 to 252 days
- 253 to 364 days
- > 364 days

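### The 52- and 104-week safety tables set crude percentages from unequal planned windows side by side (52 against 40 weeks, 104 against 92) with no exposure adjustment, and the pooled MORF-057 column is undefined

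*SAP*

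**What the plan says.** Section 4.9 fixes two observation windows for the long-term safety tables. For the groups randomized to active drug, "The safety analysis for the 52-week Treatment Period will include cumulative safety data collected during the entire 52-week Treatment Period". For the group that starts on placebo and switches to 200 mg Q.D.-E, "only safety data collected during the 40-week Maintenance Period will be included for the participants in this group", restricted to those who continued and received MORF-057. The 104-week analysis follows the same pattern: 104 weeks for Groups 1-3, and 40 + 52 = 92 weeks for Group 4.

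The measure is a count and a percentage of participants. Table 1 gives frequencies and proportions as the safety endpoint, section 4 tabulates categorical data as n (%), and section 4.9.1 counts a participant once per term. None of the adverse event tables listed in section 4.9.1 uses person-time, a time-to-event summary or a common window.

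Section 4.9 also plans a pooled display: "The safety data will be summarized by treatment groups and the pooled MORF-057 groups based on the Safety Population defined in Section 3.3". It does not list the groups that form the pool in the 52- and 104-week analyses.

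Exposure in days is derived per participant in section 4.6.1. For Group 4 the 52-week exposure summary "will include only the exposure to MORF-057 during the Maintenance Period". It is tabulated separately and is not used as a denominator for adverse events.

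**The concern.** A crude percentage of participants with an event depends on how long they were observed. Two regimens with the same event rate give different percentages if one is watched for 52 weeks and the other for 40. A second difference lies on top of this: Groups 1-3 keep participants who stopped during induction, with short exposure, while Group 4 starts only with participants who stayed through 12 weeks of placebo.

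These are the tables in which the safety of 200 mg Q.D.-E is set beside the other regimens. A reader who compares the columns could take a difference in observation time or selection for a difference between regimens. The window also acts on the table of non-serious TEAEs restricted to terms above 5%: a 52-week risk of 6% corresponds to about 4.6% over 40 weeks. If Group 4 is in the pooled column, that column mixes unequal follow-up.

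**Working it through.** **Inputs from the SAP.** Windows of 52 and 40 weeks, and of 104 and 92 weeks (section 4.9); equal randomization, 70 per group (section 1.2). The SAP states no adverse event or dropout rate, so there is no safety figure of its own to reproduce. All rates below are assumptions, set equal across groups so that any difference is an artefact.

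**1. Constant rate, full follow-up, 52-week table.** For a 52-week risk p, the weekly hazard is h = -ln(1 - p)/52 and the 40-week risk is 1 - exp(-40h). For p = 10%, h = 0.002026 and the 40-week risk is 1 - exp(-0.0810) = 7.8%.

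| Groups 1-3, 52 weeks | Group 4, 40 weeks | Ratio |
|---|---|---|
| 5% | 3.9% | 0.77 |
| 10% | 7.8% | 0.78 |
| 30% | 24.0% | 0.80 |
| 60% | 50.6% | 0.84 |

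For rare events the ratio tends to 40/52 = 0.77, an understatement of about 23%. It shrinks as events become common. The 7-day tail of the TEAE window barely matters: at 0.50 events per participant-year, 39.3% against 31.9% becomes 39.9% against 32.6%.

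**2. The 104-week table.** The limiting ratio is 92/104 = 0.885, so the understatement is at most about 12%. At 0.50 per year the percentages are 63.2% and 58.7%.

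**3. Pooled column, if Group 4 is in it.** At 0.50 per year with four equal groups: (3 × 39.35 + 31.93)/4 = 37.5%, which is the risk over neither window.

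**4. Dropout.** With weekly event hazard λ and dropout hazard d, the chance of an observed event in T weeks is P(λ, d, T) = λ/(λ + d) × [1 - exp(-(λ + d)T)]. Groups 1-3 have P(λ, d1, 12) + exp(-(λ + d1) × 12) × P(λ, d2, 40); Group 4 has P(λ, d2, 40). With λ = 0.50/52 and 30% maintenance dropout:

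| Induction dropout | Groups 1-3 | Group 4 | Ratio |
|---|---|---|---|
| 10% | 32.1% | 27.2% | 0.85 |
| 20% | 29.1% | 27.2% | 0.93 |
| 25% | 27.6% | 27.2% | 0.98 |
| 30% | 26.1% | 27.2% | 1.04 |

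Mean exposure is 41.7 against 33.6 weeks in the first row and 33.6 weeks in both columns of the last. Dropout confined to Group 4's maintenance period would widen the gap: 39.3% against 27.2%, a ratio of 0.69.

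**5. Person-time rates.** Under a constant hazard, first events divided by time at risk return the same rate in every group (50 per 100 participant-years in the example), whatever the window or dropout. Now let the hazard be four times higher in the first 12 weeks on active drug, with no dropout. The crude risk is 1 - exp(-λ(48 + m)), and mean time at risk is [1 - exp(-48λ)]/(4λ) + exp(-48λ)[1 - exp(-mλ)]/λ, with m = 40 for Groups 1-3 and m = 28 for Group 4. For later rates of 0.10 and 0.50 per year the crude ratios are 0.87 and 0.91. The exposure-adjusted rates are 17.4 against 19.5 and 97.2 against 107.5 per 100 participant-years, ratios of 1.12 and 1.11. The adjusted rate then errs the other way.

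**6. Common window.** Restricting every group to the first 40 weeks from first MORF-057 dose gives equal percentages when follow-up is complete, whatever the shape of the hazard (31.9% in each group at a constant 0.50 per year). It does not remove unequal dropout. With 30% dropout in each period, replacing 40 by 28 in the second stage of step 4 gives 22.3% for Groups 1-3 against 27.2% for Group 4. The two measures therefore cover different weaknesses.

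**The case against.** The long-term tables are descriptive, and no between-group safety test is planned. The only randomized, placebo-controlled safety comparison is the 12-week Induction Period analysis, where all four groups share one planned window. The SAP is open about restricting Group 4 to maintenance data, labels the group separately, and tabulates exposure by group; a planned 40-week period is 280 days, so the absence of Group 4 from the band above 364 days would be plain. All of this stands, and it limits the consequence. It does not let a reader convert the crude percentages into comparable ones, because the conversion depends on dropout and on the shape of the hazard.

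A reader might infer that Group 4 must look safer by construction. The documents do not support that: steps 1 and 4 show that it follows with full follow-up or modest induction dropout, and fails when induction dropout is heavy. Nor does the SAP state that Group 4 is in the pooled column. That reading is natural, since Group 4 is by then on MORF-057, but it is an inference.

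It can also be objected that exposure-adjusted rates are no cure. This is right in part: step 5 shows a bias of about 11-12% in the opposite direction under an early-peaking hazard. Rates belong beside the crude percentages and should not become the sole basis for comparison.

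**Conclusion.** The point holds in a limited form. Followed as written, the SAP yields long-term safety percentages that are not comparable between Group 4 and Groups 1-3. With an equal constant hazard and full follow-up, Group 4 is understated by up to about 23% in relative terms at 52 weeks and about 12% at 104 weeks. With 30% maintenance dropout and 0.50 events per year, the ratio of Group 4 to Groups 1-3 runs from 0.85 to 1.04 as induction dropout goes from 10% to 30%.

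Induction dropout cannot offset the difference in the additional 104-week TEAE summary of participants who entered the extension. All of them completed 52 weeks, so Groups 1-3 carry about 12 more weeks of counted time by design.

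One might go further and say that regimen selection will rest on these tables. Nothing in the SAP says so. No primary, secondary or Induction Period conclusion changes. This is a cheap improvement to descriptive tables, worth making before the 52-week database lock.

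**What to change.** For the 52- and 104-week analyses:

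- Add exposure-adjusted incidence rates beside the crude percentages: participants with a first event per 100 participant-years at risk, with 95% CI, by group and pooled. Apply them to the overall TEAE summary, serious TEAEs, TEAEs leading to treatment discontinuation and common preferred terms.
- State which groups form the pooled MORF-057 column in each analysis.
- Show the same key summaries over a common window, the first 40 weeks from first MORF-057 dose, because the rate assumes a roughly constant hazard.
- State that Group 4 is not to be compared with Groups 1-3 on crude percentages alone, and that neither added measure removes the selection of Group 4 after 12 weeks of placebo.

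The cost is one or two extra descriptive tables, built from dosing dates and event start dates for which the SAP already has derivation and partial-date rules. No new data are needed.

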#### 4.9.1. Adverse Events

Adverse events (AEs) will be coded using the Medical Dictionary for Regulatory Activities (MedDRA) dictionary (effective version at the time of database lock) by System Organ Class (SOC) and Preferred Term (PT). Grading of AE will be performed in accordance with CTCAE Version 5.0.

A treatment-emergent AE (TEAE) is defined as an AE that occurs during the period from the administration of the first dose of study drug up to 7 days after the last dose of study drug.

AEs will be classified as related or not related to the study drug by Investigator. If the relationship of an AE is missing/unknown, the AE will be considered study drug related.

The following summary tables will be presented:

- Overall Summary of TEAEs.
  - TEAE
  - Serious TEAE
  - TEAE with grade 3 or worse
  - Treatment-related TEAE
  - Treatment-related serious TEAE
  - TEAE leading to death
  - TEAE leading to permanent treatment discontinuation
- TEAEs by system organ class (SOC) and preferred term (PT).
- TEAEs by SOC, PT, and maximum Severity.
- TEAEs by SOC, PT, and relationship to Study Drug.

- Serious TEAE by SOC and PT
- Serious TEAEs by SOC, PT, and maximum Severity
- Serious TEAEs by SOC, PT, and Relationship to Study Drug
- Non-serious TEAEs (PTs with an incidence >5%) by SOC and PT
- TEAEs leading to permanent treatment discontinuation by SOC and PT

If more than one event occurred with the same PT or SOC for the same participant, the participant will be counted only once for that term.

The TEAE summaries for the 12-week Induction Period will include all TEAEs that occurs before the day of the first maintenance treatment for participants who have continued to the Maintenance Period, and all TEAEs for participants who have discontinued the study treatment before entering the Maintenance Period. If both the last induction treatment dose and the first maintenance treatment dose occur on the same day, any TEAEs reported on that day will be considered for the Maintenance Period and not included in the Induction Period Analysis, unless there is evidence to confirm that the TEAE occurred before the administration of the maintenance treatment.

In the TEAE summaries for the 52-week Treatment Period and the 104-week Total Treatment Period, for participants randomized to the placebo group during the induction period who have subsequently received MORF-057 200 mg Q.D.-E during the Maintenance Period, only the TEAEs that occurs on or after the first day of maintenance treatment dose will be included and presented in the treatment group denoted by 200 mg Q.D.-E. If both the last induction treatment dose and the first maintenance treatment dose occur on the same day, any TEAEs reported on that day will be included in the summaries for this group, unless there is evidence to confirm that the TEAE occurred before the administration of the maintenance treatment. If there are any participants who were randomized to placebo group during the Induction Period and continued to the Maintenance Period but having the actual maintenance treatment different from MORF-057 200 mg Q.D.-E by mistakes, they will not be included in the summaries but presented separately as appropriate.

In addition, the TEAE for the 104-week Total Treatment Period will be summarized based on both the safety population, and the subset of the Safety Population who have continued to the Extension Period.

The following line listings will be provided:

- Listing of all AEs
- Listing of serious TEAE
- Listing of TEAEs leading to withdrawal of study treatment
- Listing of all deaths

#### 4.9.2. Clinical Laboratory Evaluations

Observed results and changes from baseline (see Section 2.1.1) for central clinical laboratory results (hematology, coagulation, chemistry, and urinalysis) will be summarized descriptively for the on-treatment period at the scheduled visits including re-allocated visits (EOT or unscheduled, see Section 2.3).

A shift table from baseline will be used to summarize the number and percentage of participants experiencing laboratory abnormalities at each scheduled visit, as well as for the worst post-baseline values during the on-treatment period for each laboratory parameter. The determination of the worst post-baseline value will use the laboratory results from both scheduled and unscheduled visits.

The following plots will be provided:

- Mean ( $\pm$  SD) and mean change from the baseline ( $\pm$  SD) over scheduled visits for hematology parameters
- Peak alanine transaminase (ALT) or aspartate transaminase (AST) vs. peak total bilirubin post baseline

A listing will be provided for altered liver function test (i.e., participants with any elevated ALT or AST  $>3$  x ULN and associated with an increase in total bilirubin  $>2$  x ULN), including ALT, AST, Alkaline Phosphatase (ALP), and total bilirubin.

All laboratory data will be presented in a listing. Local laboratory results may be listed separately from central as appropriate, but they will not be summarized with central lab results due to calibration differences.

